Based on recommendations of the International Conference on Harmonization of Good Clinical Practice (ICH–GCP) a pre-specified detailed statistical analysis plan is conceived to prevent outcome reporting bias and data-driven analysis results [2]. The present study update and statistical analysis plan are drafted without knowledge of outcome data.

METHODS

Design

This is a single center, randomized, controlled, pragmatic trial comparing two strategies of ventilation, the conventional ventilation and the full closed loop mode, in postoperative high-risk cardiac surgery patients admitted in the intensive care unit (ICU). The trial was conducted in the ICU of the Catharina hospital in The Netherlands, a tertiary teaching hospital, specialized in cardiac surgery. The trial protocol was registered in ClinicalTrials.gov (NCT03180203) and was approved by the Medical Research Ethics Committees United (MEC-U), Nieuwegein, The Netherlands, under reference number R16.054.

Eligibility of the patients

Consecutive patients that would be admitted to receive cardiac surgery were screened for eligibility. Patients received information of the trial on the day they had their preoperative anesthesia assessment and consent was obtained the day before surgery if the patient fulfilled the inclusion and exclusion criteria. Informed consent was asked from the patient in all cases before surgery. The patient was excluded if after randomization the consent was withdrawn.

Inclusion and exclusion criteria

Inclusion criteria were an age >18 years old, elective cardiac surgery which included bypass, valve and ascending aortic surgery, a body mass index of < 35 kg/m², and postoperative treatment with mechanical ventilation on a high or intensive care unit. Exclusion criteria were, postoperative ARDS according to the Berlin definition [3], postoperative need for extracorporeal membrane

oxygenation, postoperative admission on the Post Anesthesia Care Unit (which was preoperatively determined by the anesthesiologist), a medical history containing pneumonectomy, lobectomy or chronic obstructive lung disease GOLD 3 or 4 classification, and patients participating in another postoperative study on the intensive care.

Randomization and blinding.

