A simple randomization method was used to randomly allocate patients in a 1:1 ratio to the conventional ventilation group or the INTELLiVENT-ASV group. Randomization was performed using the list randomizer on the website www.random.org. Randomization and allocation was performed immediately after the informed consent form was signed and the allocation of the patient was known only at the moment of the randomization. A hardcopy of the randomization outcome was printed with timestamp, signed and archived.

The physician and the team caring for the patients were not blinded. The researcher performing the data analyses, the radiologist that evaluates the postoperative chest X-rays, and the statistician performing the data analyses will be blinded.

The ventilation strategies

Patients randomized to the conventional ventilation group received a continuous mandatory volume or pressure controlled ventilation, if they were not breathing spontaneously, immediately after the admission in the ICU. Based on physician criterion ventilator settings were set by the anesthesiologist in consultation with the intensivist and ICU nurse on duty during the postoperative handover.

Pressure support mode was selected if patients were breathing spontaneously during handover. After the handover the ICU nurse or ICU physician could adjust ventilator settings during mechanical ventilation. If needed the ICU nurse could always consult the ICU physicians on duty. It was not possible to extubate the patient without consulting the ICU physician on duty, who made the final call to extubate. Spontaneous breathing trials (SBT) were not applied during the first three hours of mechanical ventilation. The patient was extubated without a SBT if the physicians decided that the patient could be extubated within the first three hours of mechanical ventilation. Postoperative ventilation and weaning was performed based on local hospital protocols that targets lung protective ventilations with a target tidal volume of 6ml/kg of PBW. The standard operating procedure is described in appendix 1. The predicted body weight (PBW) that is used in table 3 is calculated according to a previously used formula [5]:

- $50 + 0.91 \times (\text{centimeters of height} - 152.4)$ for male; and
- $45.5 + 0.91 \times (\text{centimeters of height} - 152.4)$ for females.

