The ventilatory variables will be extracted from the datalogger output files and transferred to the databases that will be exported for statistical analysis. After that, these study databases will be locked and exported for statistical analysis to the Academic Medical Center, Amsterdam, The Netherlands. The results of this analyses will be documented in a comprehensive database. At this stage, this last database will be locked as soon as all data are entered and all discrepant or missing data are resolved – or if all efforts are employed and remaining issues cannot be fixed. At this step, the data will be reviewed before database locking. At this stage, permission for access to the database will be removed for all investigators, and the database will be archived.

Missing data

No or minimal missing for the primary and secondary outcomes are anticipated, except for the quality and number of SpO₂ measurement in the datalogger. These measurement are assessed with fingertip pulse oximeter that sometimes cannot assess a value or the quality of the assessment is not sufficient. Breaths with missing SpO₂ or a quality of the assessment of < 51% will be excluded from the analyses of the primary and secondary outcomes where this measurements are necessary.

Sample size

A power analysis was performed using G*Power (version 3.1.9.2.; Franz Faul, Universitet Kiel, Duitsland). Based on this analysis the trial was designed to enroll at least 196 patients in total. This number of patients was expected to be sufficient to detect a reduced ventilation time of 14.0 minutes in the unacceptable zone in the INTELLiVENT-ASV group considering a common standard deviation of 10.0 minutes [4], a type I error of 5%, 95% of power, similar allocation of subjects to each group and corrected for dropouts.

Predefined statistical analysis plan

There were no major adjustments from the preliminary analysis plan, as reported previously in the online accessible protocol [1]. In accordance, all statistical analyses will be conducted according to an intention-to-treat principle, considering all patients in the treatment groups to which they were randomly assigned.

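### Exclusions that can only arise after randomisation conflict with the stated intention-to-treat analysis, and the plan does not say which rule governs the analysis set

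*Combined protocol and SAP*

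**What the plan says.** **Timing.** Under Eligibility of the patients, "consent was obtained the day before surgery if the patient fulfilled the inclusion and exclusion criteria". Under Randomization and blinding, "Randomization and allocation was performed immediately after the informed consent form was signed". That section adds that the arm was revealed at this step and no earlier. Allocation was therefore known before surgery began.

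**Exclusions.** Under Inclusion and exclusion criteria: "Exclusion criteria were, postoperative ARDS according to the Berlin definition [3], postoperative need for extracorporeal membrane" oxygenation. Neither criterion has a time window or a named assessor. Under Eligibility of the patients: "The patient was excluded if after randomization the consent was withdrawn". One inclusion criterion, "postoperative treatment with mechanical ventilation on a high or intensive care unit", is also confirmed only after surgery. The exclusion for a planned stay on the Post Anesthesia Care Unit raises no such problem, because it was settled before surgery.

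**Blinding.** "The physician and the team caring for the patients were not blinded". The next sentence says that the radiologist reading the postoperative chest X-rays, the researcher doing the data analyses and the statistician are blinded.

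**Analysis.** The section Predefined statistical analysis plan commits all analyses to intention-to-treat, "considering all patients in the treatment groups to which they were randomly assigned". The Per-protocol analysis section deals with mode crossover, death and re-sternotomy. It does not mention ARDS, ECMO or withdrawal of consent. The Trial profile section plans a CONSORT flowchart.

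**The concern.** A criterion that can be met only after randomisation is not an eligibility criterion in the usual sense. Applying it removes a randomised patient. If that patient leaves the analysis, the comparison is no longer between the groups that randomisation formed, and the label intention-to-treat does not fit.

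The open time frame adds to this. Allocated ventilation starts on arrival in the ICU (The ventilation strategies), so ARDS or need for ECMO that develops on the allocated mode would still count as postoperative. Exclusion could then depend on the treatment itself, and it could be decided by staff who know the arm.

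The primary outcome is the percentage of time in a zone defined by tidal volume, EtCO₂, peak pressure and SpO₂ (eTable 1). Patients with severe respiratory failure may plausibly have unusual values, though the documents give no data on this. ICU mortality, 30-day mortality and pulmonary complications are secondary outcomes, and there was no data monitoring board. If patients who deteriorate on a mode leave the analysis, a possible harm of that mode leaves with them.

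**Working it through.** **Step 1: the rules side by side.**

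- Consent is given and the patient is randomised the day before surgery; allocation is known from then.
- Surgery follows, then ICU admission, when the allocated mode starts.
- Postoperative ARDS or need for ECMO can be judged only after surgery, so after randomisation. With no time limit, the judgement may come before or after the allocated mode starts.
- Withdrawal after randomisation leads to exclusion, in so many words.
- The SAP analyses all patients as randomised.

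The exclusion rules and the analysis rule cannot both be applied literally. No section says which prevails, who decides, within what window, or whether removed patients are counted or replaced.

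**Step 2: which exclusions could depend on the allocated mode.** ARDS or ECMO already present at ICU admission cannot result from a mode that has not started, although an unblinded judgement could still matter. ARDS or ECMO arising afterwards could result from it. The text does not separate the two.

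**Step 3: size.** The plan gives no figure for these exclusions, so there is none to reproduce. The only design figure used is the enrolment target of 196, which at 1:1 is 98 per arm. Simple randomisation need not give exactly 98. (The 196 does not follow from the stated difference of 14 minutes, SD of 10, two-sided 5% and 95% power: 2 × (1.960 + 1.645)² × (10/14)² = 13.3, so 14 per arm before dropout. That is a separate matter.)

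If *k* patients, each *d* percentage points above their arm's mean, are removed from an arm of 98, that mean falls by *k·d*/(98 − *k*). Both *k* and *d* are assumptions:

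| *k* | *d* = 20 | *d* = 40 |
|---|---|---|
| 1 | 20/97 = 0.2 | 40/97 = 0.4 |
| 3 | 60/95 = 0.6 | 120/95 = 1.3 |
| 5 | 100/93 = 1.1 | 200/93 = 2.2 |

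**Step 4: direction.** Removing such patients from the INTELLiVENT-ASV arm only would exaggerate its benefit. Removing them from the conventional arm only would shrink it. Equal removals of similar patients from both arms would largely cancel. If the removed patients lay below their arm's mean, the signs would reverse.

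**The case against.** The strongest reply is that the plan never says ARDS or ECMO patients leave the analysis. Exclusion after randomisation is explicit only for withdrawal of consent. Eligibility was checked before consent, at least in part, and the SAP keeps everyone in the randomised group. On that reading such patients stay in. This stands as a limit: removal for ARDS or ECMO is inferred from their status as exclusion criteria. It does not remove the conflict, because a criterion that exists only postoperatively has no other evident use in a trial that randomises before surgery.

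There are also safeguards. The blinded radiologist may inform an ARDS diagnosis, the statistician is blinded, and a CONSORT flowchart is planned. These help in part. Nothing gives the radiologist the exclusion decision, the decision on ECMO is not among the blinded roles, and a flowchart reports exclusions without defining the analysis set.

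Withdrawal of consent is the weaker limb. Where permission to use the data is withdrawn, exclusion is unavoidable, and what remains is a matter of label and reporting.

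Two stronger readings are tempting. A reader might infer that exclusions were in fact made with the arm in mind; the documents show only that they could have been. A reader might also set the largest illustrative shift, 2.2 points, against the planned effect of 14/180 = 7.8 points and conclude that more than a quarter of it could be an artefact. The documents do not support that: the count and the excess are unsourced, all removals are placed in one arm, the direction is open, and 180 minutes is not everyone's denominator because the outcome window closes at extubation if that comes earlier.

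**Conclusion.** The point holds as a conflict between stated rules. Patients were randomised before surgery, two exclusion criteria can be met only afterwards and have no time limit, withdrawal after randomisation excludes, and the SAP claims that all patients are analysed as randomised. If the exclusions are applied, the set is not intention-to-treat, and removal could depend on the allocated mode and be decided without blinding.

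The number of patients affected, their arm and the direction of any bias are unknown. The 0.2 to 2.2 point range is illustrative. It rests on 98 per arm, 1 to 5 removals from one arm only, and an assumed excess of 20 to 40 points. The documents do not show that biased exclusions took place.

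The matter should be settled before database lock. The plan states that it was written without knowledge of outcome data, so a definition fixed at that stage is credible.

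**What to change.** Reconcile the eligibility sections with the intention-to-treat statement in the SAP, before database lock:

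- Define the primary set as every randomised patient who started ICU ventilation, in the randomised arm. Keep those who met the ARDS or ECMO criterion after ICU ventilation began, using the logger data available.
- Allow exclusion only for facts documented before ICU ventilation began, or where permission to use the data was withdrawn.
- Call this set modified intention-to-treat. Starting ICU ventilation is itself a post-randomisation event, so the unqualified label would not be accurate.
- In the CONSORT flowchart already planned, list every exclusion by arm, reason and timing relative to the start of ICU ventilation.

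The cost is SAP wording and a fuller flowchart. The label becomes slightly less favourable than full intention-to-treat. Logger data may be incomplete for a few patients; the documents do not say whether patients who met these criteria were logged throughout.

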19. The number of patients with postoperative pulmonary complications (like pneumonia, pneumothorax, atelectasis on the X-ray within the first 72 hours after surgery).
20. The percentage of breaths that the SpO₂ measurements were $<85\%$ according to the total number of recorded breaths (when the measured SpO₂ had a quality index of $>50\%$).
21. The percentage of breaths that the EtCO₂ and SpO₂ measurements were missing or of a quality of $<51\%$.

22. The median acceptance score (1-10) of the nurse. The answers of the whole survey will be published as supplementary data.

23. During this study the pressure, volume, flow and EtCO₂ wave patterns were recorded to analyze and detect patient-ventilator asynchronies. Currently new algorithms are developed to analyze the wave patterns in an objective and reliable manner. Based on these algorithms the research group will try to compare the number and the type of asynchronies during mechanical controlled and supportive ventilation in both groups. These outcomes will be reported in another manuscript than the outcomes described above.

Study organization

The steering committee was composed of the principal investigator that was also the local coordinating investigator and five experts in ventilator support in critically ill patients all contribute to the design and revisions of the original study protocol and the statistical analysis plan. The local coordinating investigator was responsible for administrative management and for collection and management. The local coordinating investigator was supported by six local investigators to cover in duties when the local coordinating investigator could not record the data. All local investigators were registered in the delegation log. The study was conducted according to the ICH-GCP guidelines, to guaranty integrity of data collection and to ensure timely completion of the case report forms at the bedside completed by the ventilator users.

Data collection

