The effects of the intervention on ICU length of stay will be estimated with generalized linear models considering distributions that will fit a possible heavy right-tailed distribution without zero (such as truncated Poisson, gamma distribution or inverse Gaussian), choosing the best fit according to model's deviance.

Postoperative pulmonary complications (eTable 5).

The effects of the intervention on the incidence of postoperative pulmonary complications will be reported as number and percentages and estimated with risk ratio and 95% confidence intervals calculated with Wald's likelihood ratio approximation test and with χ^2 tests for hypothesis testing.

Percentage of breaths that the EtCO₂ and/or SpO₂ measurements were missing or of a quality of < 51% (eTable 5).

The percentage of breaths that the EtCO₂ or SpO₂ measurements were missing or of a quality of < 51% will be reported as number and percentages (according to the total number of breaths and not according to the number of patients) and the effects of the intervention will be estimated with risk ratio and 95% confidence intervals calculated with Wald's likelihood ratio approximation test and with χ^2 tests for hypothesis testing.

The median acceptance score (1-10) of the nurse (eTable 5).

The median acceptance score of the nurse will be reported as mean \pm standard deviation and median (interquartile range). The effect of the intervention will be estimated with a Student's *t*-test and reported as the mean difference between

the two groups. The consistency of the findings of the Student's *t*-test will be tested using a bootstrapped Student's *t*-test with 1,000 replications. If a very nonsymmetrical distribution is found, we will use the best distribution that fits the data.

Per-protocol analysis: In creating a per-protocol population we will exclude patients who had one or more major protocol violations. Patients receiving the mode of the group that they were not assigned to will be excluded for the per-protocol analysis of the primary outcome. The patient will be included for the per-protocol analysis of the primary outcome during the first three hours, if the change in mode occurred after the first three hours of ventilation.

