All recorded time (n/hour) Median (IQR)	Mean ± SD Median (IQR)	Mean ± SD Median (IQR)	Mean difference	Mean ± SD Median (IQR)	Mean ± SD Median (IQR)	Mean difference
Times SpO₂ measurement of <85% during mechanical ventilation*						
First 3 hours (n/3 hours) Median (IQR)	Mean ± SD Median (IQR)	Mean ± SD Median (IQR)	Mean difference	Mean ± SD Median (IQR)	Mean ± SD Median (IQR)	Mean difference
All recorded time (n/hour) Median (IQR)	Mean ± SD Median (IQR)	Mean ± SD Median (IQR)	Mean difference	Mean ± SD Median (IQR)	Mean ± SD Median (IQR)	Mean difference
Lowest measured SpO ₂ over all recorded time.	Mean ± SD Median (IQR)	Mean ± SD Median (IQR)	Mean difference	Mean ± SD Median (IQR)	Mean ± SD Median (IQR)	Mean difference
Missing measurement**: all recorded time EtCO ₂	Mean ± SD Median (IQR)	Mean ± SD Median (IQR)	Mean difference	Mean ± SD Median (IQR)	Mean ± SD Median (IQR)	Mean difference
SpO ₂	Mean ± SD Median (IQR)	Mean ± SD Median (IQR)	Mean difference	Mean ± SD Median (IQR)	Mean ± SD Median (IQR)	Mean difference
Number of interventions						
First 3 hours (n/3 hours) Median (IQR)	Mean ± SD Median (IQR)	Mean ± SD Median (IQR)	Mean difference	Mean ± SD Median (IQR)	Mean ± SD Median (IQR)	Mean difference
All recorded time (n/hour) Median (IQR)	Mean ± SD Median (IQR)	Mean ± SD Median (IQR)	Mean difference	Mean ± SD Median (IQR)	Mean ± SD Median (IQR)	Mean difference
Pulmonary complication (first 72 hours)						
Pneumonia	N / Total (%)	N / Total (%)	Risk ratio	N / Total (%)	N / Total (%)	Risk ratio
Pneumothorax	N / Total (%)	N / Total (%)	Risk ratio	N / Total (%)	N / Total (%)	Risk ratio
Atelectasis	N / Total (%)	N / Total (%)	Risk ratio	N / Total (%)	N / Total (%)	Risk ratio
Overall	N / Total (%)	N / Total (%)	Risk ratio	N / Total (%)	N / Total (%)	Risk ratio
Acceptance score						
Score (1-10) Median (IQR)	Mean ± SD Median (IQR)	Mean ± SD Median (IQR)	Mean difference	Mean ± SD Median (IQR)	Mean ± SD Median (IQR)	Mean difference

*Measurement with a quality index >50%

** Measurement with a quality index <51%

eTable 6 – Intention-to treat analysis and per protocol analysis of the percentage of breaths and time in the optimal, acceptable and unacceptable zones during the first 3 hours of postoperative mechanical ventilation or extubation, and for all recorded breaths for patient who were successfully extubated before or after the median postoperative mechanical ventilation time.

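### Secondary outcome 21 (EtCO₂ and SpO₂ signal loss) has conflicting definitions and effect measures, and its table rows omit the three-hour primary window

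*Combined protocol and SAP*

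**What the plan says.** The combined protocol and SAP specifies this outcome in four places.

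- **Outcomes, secondary outcome 21:** "The percentage of breaths that the EtCO₂ and SpO₂ measurements were missing or of a quality of" below 51%. No time window is given.
- **Predefined statistical analysis plan, heading for this outcome:** "Percentage of breaths that the EtCO₂ and/or SpO₂ measurements were missing or of a quality of < 51% (eTable 5").
- **The analysis text under that heading:** "The percentage of breaths that the EtCO₂ or SpO₂ measurements were missing or of a quality of" below 51%. The count is taken "according to the total number of breaths and not according to the number of patients", and the arms are compared by a risk ratio with a 95% confidence interval and a χ² test.
- **eTable 5, to which that heading points:** a block labelled "Missing measurement: all recorded time", with one row for EtCO₂ and one for SpO₂. Each row shows mean ± SD, median (IQR) and a mean difference. There is no combined row and no risk ratio. The footnote reads "Measurement with a quality index <51" percent.

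The Missing data section says "No or minimal missing for the primary and secondary outcomes are anticipated, except for the quality and number of SpO₂ measurement in the datalogger". It then excludes breaths with missing SpO₂, or SpO₂ of quality below 51%, from the primary and secondary analyses that need SpO₂. eTable 1 uses SpO₂ to define the ventilation zones, so the primary outcome is one of these.

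**The concern.** Breaths in which both signals fail, breaths in which at least one fails, and each signal counted on its own are different numerators. The analysis text and the table also disagree on the unit and the effect measure. A pooled-breath risk ratio weights patients by their number of breaths, and its χ² test treats breaths from one patient as independent. The table's mean ± SD implies one value per patient. An analyst following the text and one following the table would report different quantities.

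What is at stake is limited but specific. SpO₂ loss is the one data problem that the plan expects, and it decides which breaths enter the primary outcome. Outcome 21 is the only planned comparison of that loss between arms. The primary outcome covers the first three hours or the time to extubation, whereas the eTable 5 rows cover all recorded time only.

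**Working it through.** **Inputs.** The documents give no expected loss rate for either signal and no figure for their overlap, so there is no stated figure to reproduce. Every rate below is an assumption.

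**Bounds that need no assumed rate.** Let pE and pS be the EtCO₂ and SpO₂ loss rates.

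- P(*and*) ≤ min(pE, pS)
- P(*or*) = pE + pS − P(*and*) ≥ max(pE, pS)
- Hence P(*or*)/P(*and*) ≥ max(pE, pS)/min(pE, pS)

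The Missing data section expects little loss except for SpO₂. If that is right, the joint version is capped at the small EtCO₂ loss, while the union version is at least the whole SpO₂ loss.

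**Size under assumed rates.** With correlation φ between the two losses, P(*and*) = pE·pS + φ·√[pE(1−pE)·pS(1−pS)].

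| pE, pS | φ | *and* | *or* | ratio |
|---|---|---|---|---|
| 1%, 5% | 0 | 0.05% | 5.95% | 119 |
| 2%, 10% | 0 | 0.20% | 11.8% | 59 |
| 2%, 10% | 0.3 | 1.46% | 10.5% | 7.2 |
| 5%, 20% | 0 | 1.0% | 24.0% | 24 |
| 5%, 20% | 0.3 | 3.6% | 21.4% | 5.9 |
| 20%, 30% | 0.3 | 11.5% | 38.5% | 3.3 |
| 10%, 10% | 1 | 10% | 10% | 1.0 |

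Worked line (5%, 20%, φ = 0.3): 0.05 × 0.20 + 0.3 × √(0.0475 × 0.16) = 0.0100 + 0.0262 = 0.0362. The union is 0.25 − 0.0362 = 0.2138, and the ratio is 5.9.

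**Can the arm comparison change direction?** Only in particular cases.

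- *Signals moving in opposite directions, independent losses.* Arm A has pE 2%, pS 20%; arm B has pE 6%, pS 12%. *And*: 0.40% v 0.72%, B/A = 1.80. *Or*: 21.60% v 17.28%, B/A = 0.80. The separate rows give 6/2 = 3.0 for EtCO₂ and 12/20 = 0.60 for SpO₂.
- *Overlap differing between arms.* Arm A has 5%, 20%, φ = 0; arm B has 5%, 15%, φ = 0.3. *And*: 1.00% v 3.08%, B/A = 3.08. *Or*: 24.0% v 16.9%, B/A = 0.70.
- *Independent losses, both lower in the same arm.* No reversal is possible, because pE·pS and pE + pS − pE·pS both rise with each rate.

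**Window.** In eTable 5 the blocks for alarms, for SpO₂ below 85% and for interventions each have a first-three-hours row and an all-recorded-time row. The missing-measurement block has only the latter.

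**The case against.** The strongest reply is that the plan already contains the right definition. In outcome 21, *and* need not mean that both signals fail on the same breath. It can mean that each signal is reported, which is how eTable 5 is laid out. Because that table shows SpO₂ by arm on its own row, a large SpO₂ imbalance would be visible. This is a fair reading and it removes much of the worry. It does not remove the *and/or* and *or* wording of the analysis section, or that section's pooled-breath risk ratio, which has no place in the table.

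A reader might also infer from the footnote that a breath with no reading goes uncounted, since only a quality index is named. The block is labelled as missing measurement, so label and footnote together can be read as missing or of low quality. The documents do not say how the datalogger codes an absent reading. This supports a clarification and no more.

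Finally, all recorded time includes the first three hours and outcome 21 names no window, so the absent three-hour rows are not a contradiction. That is correct. They are an omission, notable because the neighbouring blocks have such rows and because the SpO₂ exclusion acts on the primary window.

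**Conclusion.** Outcome 21 has conflicting definitions and two effect measures, and no text says which prevails. The point is minor. It does not change the primary estimate, the sample size, alpha or the SpO₂ exclusion rule.

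A reader might infer that the reported rate will change many-fold, that the arms will change places, or that an imbalance will be presented as balance. The documents do not support these readings. No loss rates are given, the *or*/*and* ratio runs from 1.0 (equal rates, full overlap) to over 100 (low, independent losses), and a reversal needs opposite movements of the signals or different overlap between arms. If eTable 5 is followed, the SpO₂ comparison is shown separately.

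What stands without assumed rates is the pair of bounds, the mismatch between pooled-breath and per-patient analysis, and the lack of a between-arm report of SpO₂ loss for the primary window.

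**What to change.** - In secondary outcome 21, in the analysis section and in eTable 5, define two separate outcomes: the percentage of each patient's recorded breaths with (i) SpO₂ and (ii) EtCO₂ missing or of quality below 51%. Remove the combined *and*, *or* and *and/or* wording.
- In the analysis section, replace the pooled-breath risk ratio and χ² test with the per-patient mean difference that eTable 5 already shows.
- Word the eTable 5 footnote as *missing or quality index <51%*.
- Report both rows for the first three hours (or until extubation, if earlier) as well as for all recorded time.

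The cost is a wording change and two extra table rows, from breath-by-breath data already recorded by the datalogger.
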